Appendix B Tanner stages

The Tanner stages assessment for each patient at each site should be performed, if possible by the same investigator/designee trained to assess pubertal development (1, 2).

- Boys development of external genitalia
 - Stage 1: Pre-adolescent. Testes, scrotum, and penis are of about the same size and proportion as in early childhood.
 - Stage 2: The scrotum and testes have enlarged and there is a change in the texture of the scrotal skin. There is also some reddening of the scrotal skin.
 - Stage 3: Growth of the penis has occurred, at first mainly in length but with some increase in breadth. There has been further growth of testes and scrotum.
 - Stage 4: Penis further enlarged in length and breadth with development of glans. Testes and scrotum further enlarged. There is also further darkening of the scrotal skin.
 - Stage 5: Genitalia adult in size and shape. No further enlargement takes place after Stage 5 is reached.

• Girls - breast development

- Stage 1: Pre-adolescent; elevation of papilla only.
- Stage 2: Breast bud stage; elevation of breast and papilla as a small mound, enlargement of areola diameter.
- Stage 3: Further enlargement of breast and areola, with no separation of their contours.
- Stage 4: Projection of areola and papilla to form a secondary mound above the level of the breast.
- Stage 5: Mature stage; projection of papilla only, due to recession of the areola to the general contour of the breast.

• Boys/Girls - pubic hair

- Stage 1: Pre-adolescent; the vellus over the pubes is not further developed than that over the anterior abdominal wall, ie, no pubic hair.
- Stage 2: Sparse growth of long, slightly pigmented, downy hair, straight or only slightly curled, appearing chiefly at the base of the penis (boys) or along the labia (girls).
- Stage 3: Considerably darker, coarser, and more curled. The hair spreads sparsely over the junction of the pubes.
- Stage 4: Hair is now adult in type, but the area covered by it is still considerably smaller than in most adults. There is no spread to the medial surface of the thighs.
- Stage 5: Adult in quantity and type, distributed as an inverse triangle of the classically feminine pattern (girls). Spread to the medial surface of the thighs, but not up the linea alba or elsewhere above the base of the inverse triangle.

BIBLIOGRAPHIC REFERENCES

Appendix C Cogstate battery test

The Cogstate battery test will include a detection test, identification test, one card learning test, and Groton maze learning test. These individual tests assess maturing cognition across a broad number of key developmental functions such as processing speed, attention, visual learning and executive functioning, respectively. Details of the Cogstate battery test are provided in the description subsection below. Briefly, the battery of tests is administered by trained clinical site personnel and will take the patient approximately 16 to 19 minutes to complete. It will be administered electronically and is standardized. The results will be automatically calculated. The results will not be used for detection of adverse events and will not trigger further consultation or investigation.

Cogstate battery test description:

• Detection (DET; Psychomotor Function)

The Detection test is a measure of psychomotor function and uses a well-validated simple reaction time paradigm with playing card stimuli. In this test, the playing cards all depict the same joker. The subject is asked to press the **Yes** key as soon as the card in the center of the screen turns face up. The software measures the speed and accuracy of each response.

Duration of Test: 3 minutes

• Identification (IDN; Attention)

The Identification test is a measure of visual attention and uses a well-validated choice reaction time paradigm with playing card stimuli. In this test, the playing cards are all either red or black jokers. The subject is asked whether the card displayed in the center of the screen is red. The subject responds by pressing the **Yes** key when the joker card is red and **No** when it is black. The software measures the speed and accuracy of each response.

Duration of Test: 3 minutes

• One Card Learning (OCL; Visual Learning)

The One Card Learning test is a measure of visual learning and uses a well-validated pattern separation paradigm with playing card stimuli. In this test, the playing cards are identical to those found in a standard deck of 52 playing cards (without the joker cards). The subject is asked whether the card displayed in the center of the screen was seen previously in this test. The subject responds by pressing the **Yes** or **No** key. The software measures the speed and accuracy of each response.

Duration of Test: 6 minutes

• The Groton Maze Learning Test (GML; Executive Function)

The Groton Maze Learning test is a measure of problem solving and reasoning and uses a well-validated maze learning paradigm. In this test, the subject is shown a 10×10 grid of boxes on a computer screen. A 28-step pathway is hidden among these 100 possible locations. Each box represents move locations, and the grid refers to the box array (ie, 10×10). Subjects are required to find the hidden pathway guided by four search rules. These rules are: do not move diagonally, do not move more than one box (ie, do not jump), do not move back on the pathway, and return to the last correct location after an error. At each step only the most recently selected box is shown. Feedback is given with visual and auditory cues (green check marks and red crosses) to indicate whether the selected box is correct or incorrect. The head of path, or the last correct location, flashes with a green check when two errors are made in succession to indicate to the subject that they must return to this location. There are [20] well-matched alternate pathways available. The software records each move as an error or as a correct move.

Duration of Test: 7 minutes

Appendix D Guidance on contraceptive methods and collection of pregnancy information

Reproductive potential (WOCBP)

A woman is considered of reproductive potential (WOCBP), ie, fertile, following menarche and until becoming postmenopausal unless permanently sterile. Permanent sterilization methods include hysterectomy, bilateral salpingectomy and bilateral oophorectomy.

CONTRACEPTIVE GUIDANCE

Sexual counseling should be provided to patients when indicated.

Female subjects:

Highly Effective Contraceptive Methods That Are User Dependent

*Failure rate of <1% per year when used consistently and correctly*⁶

- Combined (estrogen- and progestogen-containing) hormonal contraception associated with inhibition of ovulation:
 - Oral,
 - Intravaginal,
 - Transdermal.
- Progestogen-only hormone contraception associated with inhibition of ovulation:
 - Oral,
 - Injectable.

Highly Effective Methods That Are User Independent

- Implantable progestogen-only hormone contraception associated with inhibition of ovulation.
- Intrauterine device (IUD).
- Intrauterine hormone-releasing system (IUS).

Sexual abstinence

Sexual abstinence is considered a highly effective method only if defined as refraining from heterosexual intercourse during the entire period of risk associated with the study drug. The reliability of sexual abstinence needs to be evaluated in relation to the duration of the study and the preferred and usual lifestyle of the subject.

⁶ Typical use failure rates may differ from those when used consistently and correctly. Use should be consistent with local regulations regarding the use of contraceptive methods for subjects participating in clinical studies.

COLLECTION OF PREGNANCY INFORMATION

Female subjects who become pregnant

- The Investigator will collect pregnancy information on any female subject, who becomes pregnant while participating in this study.
- Information will be recorded on the appropriate form and submitted to the Sponsor within 24 hours of learning of a participant's pregnancy.
- Participant will be followed to determine the outcome of the pregnancy. The Investigator will collect follow-up information on participant and neonate, which will be forwarded to the Sponsor. Generally, follow-up will not be required for longer than 6 to 8 weeks beyond the estimated delivery date.
- Any termination of pregnancy will be reported, regardless of fetal status (presence or absence of anomalies) or indication for procedure.
- In this study pregnancy is considered to be an AESI and will be reported as such, any pregnancy complication or elective termination of a pregnancy will be reported as an AE or SAE.
- A spontaneous abortion is always considered to be an SAE and will be reported as such.
- Any SAE occurring as a result of a post-study pregnancy which is considered reasonably related to the study treatment by the Investigator, will be reported to the Sponsor as described in Section 10.4. While the Investigator is not obligated to actively seek this information in former study subjects, he or she may learn of an SAE through spontaneous reporting.

Male subjects with partners of reproductive potential who become pregnant

- The Investigator will attempt to collect pregnancy information on any female partner of a male study subject who becomes pregnant while participating in this study. This applies only to subjects who receive study treatment.
- After obtaining the necessary signed informed consent from the pregnant female partner directly, the Investigator will record pregnancy information on the appropriate form and submit it to the Sponsor within 24 hours of learning of the partner's pregnancy.
- Partner will also be followed to determine the outcome of the pregnancy. Information on the status of the mother and child will be forwarded to the Sponsor.
- Generally, follow-up will be no longer than 6 to 8 weeks following the estimated delivery date. Any termination of the pregnancy will be reported regardless of fetal status (presence or absence of anomalies) or indication for procedure.

Appendix E Flow mediated dilatation exploratory sub-study of EFC14643 protocol

Protocol Number: Exploratory Sub-study of EFC14643 Protocol: Flow Mediated Dilatation (FMD) Sub-study

SUBSTUDY PROTOCOL ACKNOWLEDGEMENT

I have read this exploratory sub-study of EFC14643 protocol: FMD sub-study, and understand that it and an accompanying additional informed consent must be reviewed by the Institutional Review Board/Ethics Committee overseeing the conduct of the study and approved or given favorable opinion before implementation.

Introduction

The healthy endothelium plays a principal role in keeping arterial homoeostasis. Many of its functions are controlled by the bioavailability of nitric oxide, including inflammation, adhesion, coagulation, smooth muscle cell proliferation, and vasomotion (1). The vascular endothelial layer has anti-atherogenic properties. However, this physiological atheroprotective function of the endothelium can be diminished in the presence of atherosclerotic risk factors and toxic substances and conditions (2). The diminution of endothelial function may play a role in atherogenesis, which may occur before structural and clinical atherosclerosis (3). In addition to being an early event in atherogenesis, endothelial dysfunction is influential in the later stages of atherosclerotic diseases, predisposing individuals to complications, such as thrombotic events. Endothelial dysfunction is characterized by reduced bioavailability of nitric oxide through decreased production and/or increased degradation of nitric oxide. Even with adequate production, nitric oxide may not reach its biological targets (vascular smooth muscle and circulating cells) to exert its effect because of the lack of its bioavailability. In hyperlipidemia, excess LDL synthesis increases the formation of oxidized LDL. The resultant increase of oxidative stress enhances nitric oxide destruction, thereby reducing its biological effects and attenuating endothelium-dependent vasodilation (4).

Flow-mediated dilatation (FMD) measures the vasomotor effects of this modification in the phenotype of the arterial wall and can therefore be used to study the vascular biology of atherosclerosis as it progresses from childhood (5). Over the past several decades, a noninvasive technique has matured to evaluate FMD, an endothelium-dependent function, in the brachial artery. This stimulus incites the endothelium to release nitric oxide (NO) with resultant vasodilation that can be imaged and quantitated as an index of vasomotor function (6). The use of ultrasound to assess FMD is noninvasive, and safe and has been applied in prior clinical trial in a similar setting (7). The test is based on the measurement of the brachial artery diameter at baseline and after an increase in blood flow caused by inflating and then deflating a forearm blood pressure cuff. In this test, the proportional increase in luminal diameter induced by hyperemia is calculated and used as a marker of systemic endothelial function.

In the general population, several risk factors that are associated with CVD such as hypertension, diabetes, hyperlipidemia, hyperhomocysteinemia, inflammation, advanced age, and cigarette smoking have been associated with impairment in FMD prior to vascular disease (8).

Improvement in endothelial function has been noted following statin treatment in adults with coronary artery disease and in asymptomatic patients with cardiovascular risk factors (9). While most factors, which improve endothelial function, have been shown to be of cardiovascular benefit, exceptions include antioxidant supplementation and hormone replacement therapies. These 2 later agents have shown improvement in endothelial function but without corresponding cardiovascular benefit.

The negative effect of cholesterol on endothelial function was initially observed in pediatric patients with heFH from as early as 8 years of age (4). In this study, the degree of endothelial impairment as measured by FMD obtained via high resolution ultrasound correlated with both LDL-C and Lp(a) levels. Other studies have also shown that children with heFH have reduced endothelial function (as measured by FMD) as compared to healthy controls and that the degree of endothelial function was worse in the patients who had a family history of premature CVD (8).

Early simvastatin therapy of 10 to 40 mg daily restores endothelial function in 28 weeks in 9- to 18-year-old children with heFH (10) as measured by FMD of the brachial artery. However, despite this promising result whether an improvement in endothelial function during childhood will translate into decreased risk of future cardiovascular disease is unknown (7).

Primary objective

To explore the effect of alirocumab versus placebo on endothelial function after 24 weeks of treatment in heterozygous familial hypercholesterolemia (heFH) patients aged of 8 to 17 years on optimal stable daily dose of statin therapy \pm other lipid modifying therapies (LMTs) or a stable dose of non-statin LMTs in case of intolerance to statins.

Study design

Select sites from the EFC14643 trial, will be asked to participate in the sub-study. Study centers that have access to the assessment of FMD will be approached. These centers that are willing to take part in the sub-study must undergo further qualification. Sites selected to participate in the sub-study will have IRB/EC approval for the main EFC14643 study and for the sub-study and an additional informed consent.

Patients who have provided signed informed consent for the main study of the EFC14643 trial at these select sites will be asked to participate in the sub-study. The participation in the sub-study is voluntary and declining participation in the sub-study does not prevent participation in the main study. Once the additional written informed consent is obtained for the sub-study and if patients fulfil the additional eligibility criteria for the sub-study, then they will undergo a baseline FMD assessment during the screening period. The patients will undergo a second FMD assessment at Week 24.

A standardized setting for testing will be implemented (11). Experienced ultrasonographers who will be involved in image acquisition will be trained prior to undertaking FMD assessments. The same scanning protocol will be employed at all sites. The same trained ultrasonographer should perform the FMD assessment at baseline and Week 24 on the patient, if at all possible. A central reading lab will review and analyze the images. Details will be provided in separate study related

Amended Clinical Trial Protocol 03 EFC14643 - alirocumab 06-Jan-2021 Version number: 1

documents. As the FMD assessment will take place during the double-blind treatment period, the personal involved in the FMD assessments will be blinded, including the central reading lab.

To assess brachial FMD, the brachial artery diameter will be measured both at rest and during the reactive hyperemia. Reactive hyperemia will be induced by sphygmomanometer or equivalent placed around the forearm, followed by release. The vessel diameter after reactive hyperemia will be expressed as the percentage relative to the resting scan (ie, [lumen diameter after reactive hyperemia – lumen diameter at rest]/lumen diameter at rest *100). The per cent maximum flow meditated dilatation of the brachial artery measured via ultrasound will be determined by a central reading laboratory with pre-specified methodology as detailed in the study related documents.

Primary endpoint

The absolute change from baseline to Week 24 in flow mediated dilatation of the brachial artery (as determined by the central reading laboratory) regardless of adherence to treatment (ITT estimand).

Study procedures

Each patient will undergo an FMD assessment at baseline and at Week 24. The baseline FMD assessment can be done at Week -2, Week -1 or another day of the screening period, or on Day 1, but prior to randomization into the main EFC14643 study. The Week 24 FMD assessment can be done on the same day as the Week 24 visit or at an alternative day corresponding to the time window (+/- 3 days) of the main EFC14643 study. However, the Week 24 FMD assessment must be done prior to entry into the open label treatment period.

Numerous factors affect flow mediated vascular reactivity. Thus, patients will need to comply with more details provided in the consent form. Briefly, patients will need to be fasting for at least 8 to 12 h before the FMD assessment. All vasoactive medications should be withheld for at least four half-lives, if possible. In addition, subjects will be asked to refrain from exercise and should not ingest substances that might affect FMD such as caffeine, high-fat foods and vitamin C or use tobacco for at least 4 to 6 h before the study.

The site will have access to an ultrasound system with specific equipment requirements as detailed in the study related documents. The same scanning protocol (which will be provided in study related documents) will be implemented across sites. During the procedure, the subject will be supine with the arm in a comfortable and outstretched position. A sphymomanometric cuff or equivalent will be placed on the forearm. After the patient has an adequate period of rest (which will be standardized), a baseline rest image and associated data will be acquired by the trained operator. Thereafter, arterial occlusion is created by cuff inflation or equivalent. Deflation of the cuff or equivalent will induce a brief high flow state through the brachial artery (reactive hyperemia) to accommodate the resistance vessels. The resulting increase in shear stress causes the brachial artery to dilate. An image and associated data will be acquired during this reactive hyperemia period. The total duration of the FMD assessment at either baseline or Week 24 is expected to be approximately 30 minutes.

Selection of patients

Additional inclusion criteria:

• A signed informed consent for FMD sub-study of EFC14643 protocol indicating parental permission with or without patient assent, depending on capacity for understanding based on developmental maturity. In cases involving emancipated or mature minors with adequate decision-making capacity, or when otherwise permitted by law, a signed informed consent directly from patients.

Additional exclusion criteria:

- Patients who withdraw consent for FMD sub-study of EFC14643 protocol during the screening period (patient who is not willing to continue or anticipated not to continue).
- Patients who are anticipated to have difficulty with complying with the procedure for the FMD assessment, based on Investigator judgment.
- Patients who are anticipated to require prohibited new (ie, treatment initiated after Week 0 FMD and until Week 24 FMD) concomitant medications.
- Patients who have initiated treatment with prohibited new concomitant medications within the past 4 weeks from the Week 0 FMD.

Patients who are not eligible for the sub-study based on the additional eligibility criteria may still take part in the main study of the EFC14643 protocol.

Prohibited new concomitant medications

Patients should avoid **new** treatment with the following medications as they may confound the results of the FMD (9):

- Vitamin C
- Vitamin E
- Angiotensin Converting Enzyme (ACE) inhibitors
- Angiotensin Receptor Blockers (ARBs)
- Estrogen

Patients, who are already taking the above concomitant medications prior to the Week 0 FMD assessment, may continue to take these medications during the study only if they will continue them at a stable dose until the Week 24 FMD assessment.

Handling of patient after permanent treatment discontinuation and of patient study discontinuation

Patients who wish to withdraw their participation in this sub-study may do so at any time. If they do so, they may continue participation in the main study. Patients, who discontinue the main study, must also discontinue participation in the sub-study.

Patients, who prematurely discontinue study treatment (regardless of the reason) and continue the main study, should be encouraged to complete the scheduled Week 24 FMD assessment.

Statistical considerations

Sample Size Determination and Randomization:

Assuming that 30 to 39 patients (regardless of the dosing regimen cohort: 20 to 26 in the alirocumab group and 10 to 13 in the placebo group) will participate to the sub-study, the statistical power to demonstrate superiority of alirocumab versus placebo at 0.05 two sided significance level is provided in Table 1 according to several assumptions for the mean difference and standard deviation (SD) of the absolute change from baseline to Week 24.

Table 1 - Statistical power according to mean difference and SD of the FMD absolute change from
baseline to Week 24

Expected number of patients (2:1 ratio)	Standard	Delta mean (%)		
	deviation (%)	2	2.5	3
30	2.5	51%	70%	84%
	4	23%	34%	46%
39	2.5	63%	81%	93%
	4	29%	43%	57%

Analysis:

The absolute change from baseline in FMD at Week 24 will be analyzed using an ANCOVA model. The model will include the fixed categorical effects of treatment group (alirocumab, placebo), the dosing regimen cohorts (Q2W, Q4W), the treatment by dosing regimen cohort interaction and the continuous fixed covariate of baseline FMD value. Model assumptions for normality will be explored prior to the analysis testing. Throughout the ANCOVA model, least-square (LS) mean and standard error (SE) will be provided for each treatment group and LS means difference will be provided for the comparison of the alirocumab group versus the placebo group with the 95% CI, using appropriate contrasts.

All Week 24 FMD values will be included in the analysis regardless of individual patient adherence to treatment.

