Genotyping for heFH will be conducted from a specimen of whole blood, saliva, or buccal swab in patients consenting to undergo genotyping testing. This test will be recommended for all patients but will be mandatory only for patients without clinical diagnosis or no previous documented genotyping. In case of non-mandatory genotyping the sample could be taken preferentially during the screening period but could be done at any visit during the double-blind treatment period.

Randomization will be stratified according to previous participation (yes or no) in the Phase 2 DFI14223 study and baseline BW ($<50 \text{ or } \ge 50 \text{ kg}$).

The study consists of a run-in period (as needed), screening period, double-blind treatment period, and an open label treatment period.

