For the Q2W dosing regimen cohort, multiple imputations will be used with different imputation strategies applied to LDL-C values missing during the on-treatment period (ie, within the time period from the first double-blind IMP injection up to the day of last double-blind injection +21 days) versus LDL-C values missing after treatment discontinuation (ie, after the day of last double-blind injection +21 days) based on the following assumptions:

- Patients within 21 days of their last double-blind IMP injection would continue to show benefit from treatment similar to that observed at the scheduled time point. Therefore, LDL-C values missing during the on-treatment period (eg, samples obtained out-side the specified window, no blood sample available although visit was performed, etc.) should be considered "Missing At Random" and imputed based on other on-treatment measurements.
- Patients who stopped taking their study treatment no longer benefited from it after discontinuation, and thus tended to have LDL-C values returning to baseline. Therefore, LDL-C values missing more than 21 days after treatment discontinuation should be imputed based on patient's own baseline value.

For patients who permanently discontinued the treatment due to the COVID-19 pandemic, missing post-treatment data will be considered "Missing at Random" and imputed based on other on-treatment measurements in the same treatment group.

Missing LDL-C values will be imputed 100 times to generate 100 complete data sets. The percent change from baseline to Week 24 will be derived from observed and imputed LDL-C at this time point. The completed data sets will be analyzed using an ANCOVA model, with unequal variances by treatment group (except if convergence issue), with treatment group (alirocumab, placebo) and randomization strata (previous participation [yes or no] to DFI14223 study, baseline body weight [<50 or \geq 50 kg]) as fixed effects, and the baseline LDL-C value as continuous covariate. The results from the 100 analyses will be combined using Rubin's formulae (8).

For the Q4W dosing regimen cohort, the same approach will be taken with the following differences:

- The on-treatment period will be defined as the time period from the first IMP injection up to the day of the last double-blind injection +35 days for patients with a last double-blind injection before the switch to Q2W regimen (actual of sham), +21 days otherwise.

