- The ANCOVA model will include treatment group (alirocumab, placebo) and randomization strata (baseline body weight [<50 or ≥50 kg]) as fixed effects, and the baseline LDL-C value as continuous covariate.

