2.4.4.4 Exploratory efficacy analyses

Difference in percent change in LDL-C between the 2 alirocumab Q2W and Q4W dosing regimen cohorts

The difference in terms of percent change in LDL-C between the 2 alirocumab dosing regimen groups will be explored in the ITT population and in the mITT population.

FMD sub-study

The absolute change from baseline in FMD at Week 24 in the FMD sub-study population will be analyzed using an ANCOVA model, with unequal variances by treatment group (except if convergence issue). The model will include the fixed categorical effects of treatment group (alirocumab, placebo), the dosing regimen cohort (Q2W, Q4W) the treatment-by-dosing regimen cohort interaction and the continuous fixed covariate of baseline FMD value. Model assumptions for normality will be explored prior to the analysis testing. Throughout the ANCOVA model, least-square (LS) mean and standard error (SE) will be provided, regardless of the dosing regimen cohort, for the alirocumab group and the placebo group. LS means difference will be provided for the comparison of the alirocumab group versus the placebo group regardless of the dosing regimen cohorts with the 95% CI, using appropriate contrasts.

All Week 24 FMD values will be included in the analysis regardless of individual patient adherence to treatment.

In addition, the same statistical approach as described above will be applied but only including ontreatment values in the model (on-treatment analysis).

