2.4.5.7 Analyses of Cogstate Battery test

Cognitive scores (including by domains: DET [Psychomotor Function], IDN [Attention]; [OCL; Visual Learning]; GML [Executive Function]) and composite score will be described on the safety population by treatment for the double-blind period.

The change from baseline will be described for each score and the composite score.

The absolute change from baseline in the composite score at Week 24 will be analyzed using an ANCOVA model, with unequal variances by treatment group (except if convergence issue). The model will include the fixed categorical effects of treatment group (alirocumab, placebo), the dosing regimen cohort (Q2W, Q4W), the treatment-by-dosing regimen cohort interaction, the randomization strata and the continuous fixed covariate of baseline composite score value. Model assumptions for normality will be explored prior to the analysis testing. Throughout the ANCOVA model, least-square (LS) mean and standard error (SE) will be provided for each treatment group (placebo, alirocumab) regardless of the dosing regimen cohorts. LS means difference will be provided for the comparison of the alirocumab group versus the placebo group regardless of the dosing regimen cohorts, with the SE, 95% confidence intervals (CI) for descriptive purpose, using

appropriate contrasts. The corresponding effect sizes will be computed using Cohen's formulae (see Appendix G).

For the OL period, the results will be described overall in the OL population.

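### The FMD sub-study ANCOVA leaves out the body-weight randomisation stratum without a stated reason, which may cost precision but causes neither average bias nor type I error inflation

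*Protocol*

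**What the plan says.** Protocol 6.1 states: "Randomization will be stratified according to previous participation (yes or no) in the Phase 2 DFI14223 study and baseline BW" (<50 or ≥50 kg).

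The FMD model is the same in both documents. After treatment group and dosing cohort, Protocol Appendix E lists "the treatment by dosing regimen cohort interaction and the continuous fixed covariate of baseline FMD value", and SAP 2.4.4.4 lists "the treatment-by-dosing regimen cohort interaction and the continuous fixed covariate of baseline FMD value". The SAP adds unequal variances by treatment group and applies the same model to an on-treatment analysis. No randomisation stratum appears.

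The closest comparable model is the Cogstate composite-score ANCOVA in SAP 2.4.5.7. It is also pooled over cohorts and also allows unequal variances. Its terms after treatment and cohort are "the treatment-by-dosing regimen cohort interaction, the randomization strata and the continuous fixed covariate of baseline composite score value".

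In SAP 2.4.4.1.4 the pattern-mixture ANCOVA for Q2W includes "randomization strata (previous participation [yes or no] to DFI14223 study, baseline body weight". For Q4W, the text reads "The ANCOVA model will include treatment group (alirocumab, placebo) and randomization strata (baseline body weight". The primary MMRM, the robust regression and the logistic regression (SAP 2.4.4.1.1, 2.4.4.2.2 and 2.4.4.2.3) also account for strata.

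The sub-study expects 30 to 39 patients, split 20:10 to 26:13, who volunteer at selected sites (Appendix E). The analysis set needs both a baseline and a post-baseline scan (SAP 2.3.1.3).

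**The concern.** The usual practice is to analyse by the factors used to randomise, and this trial does so nearly everywhere else. If a stratification factor is prognostic and left out, one of two things happens. If the arms are balanced on it, the residual variance still carries its effect, so the standard error is too large and the test is conservative. If they are not balanced, the estimate is noisier than it need be.

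The sub-study is small and self-selected, so balance in the full trial does not guarantee balance here. At 20:10, moving one heavier child from one arm to the other changes the between-arm gap in the share ≥50 kg by 1/20 + 1/10 = 15 percentage points.

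An oversight is plausible. Protocol amendment 03 added the cohort terms to this same model because they had been left out by mistake, and SAP version 2 reopened the model to add unequal variances.

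**Working it through.** **Inputs from the documents.** N = 30 (20:10) or 39 (26:13), two-sided alpha 0.05, mean difference δ = 2, 2.5 or 3, SD 2.5 or 4 (Appendix E).

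**Assumptions, because the documents give no figures.** Share of children ≥50 kg: 30 to 50%. Difference g in FMD change between weight strata, given baseline FMD: 0 to 3 points. Share of residual variance explained by weight, R²: 0 to 20%. All calculations use a common variance, whereas the SAP plans unequal variances.

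**Step 1: reproduce the plan's power table.** SE = SD·√(1/n₁ + 1/n₂), noncentrality = δ/SE, noncentral t with N−2 degrees of freedom.

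| N | SD | SE | Stated (δ = 2 / 2.5 / 3) | Recomputed |
|---|---|---|---|---|
| 30 | 2.5 | 0.97 | 51 / 70 / 84% | 51.4 / 70.3 / 84.9% |
| 30 | 4 | 1.55 | 23 / 34 / 46% | 23.9 / 34.4 / 46.4% |
| 39 | 2.5 | 0.85 | 63 / 81 / 93% | 63.1 / 81.8 / 93.1% |
| 39 | 4 | 1.36 | 29 / 43 / 57% | 30.0 / 43.3 / 57.6% |

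All 12 cells agree within 1 point. The table stands.

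**Step 2: chance imbalance if allocation ignored weight (worst case).** Using the hypergeometric distribution, the between-arm difference in the share ≥50 kg has SD 0.18 to 0.20 at N=30 and 0.16 to 0.17 at N=39. A difference of at least 20 points has probability 18 to 27% across these settings.

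**Step 3: effect on one estimate.** Shift = imbalance × g. A 20-point imbalance gives 0.2 × 1 = 0.2, 0.2 × 2 = 0.4 or 0.2 × 3 = 0.6 points. Against SE 0.97 (N=30, SD 2.5), that is 0.21, 0.41 or 0.62 of a standard error.

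**Step 4: simulation of the planned terms with and without weight** (4,000 runs per setting, total SD 2.5, no treatment effect, half the children in each stratum). Here weight explains g²/4 ÷ 6.25 of the variance: 4% at g=1 and 16% at g=2.

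| N | g | Weight balanced by allocation? | Empirical SE, without → with weight | Type I error, without → with weight |
|---|---|---|---|---|
| 30 | 0 | no | 1.015 → 1.036 | 4.8 → 4.7% |
| 30 | 1 | no | 1.009 → 1.010 | 4.9 → 5.0% |
| 30 | 2 | no | 1.021 → 0.954 | 4.6 → 5.4% |
| 30 | 2 | yes | 0.920 → 0.910 | 3.3 → 5.0% |
| 39 | 0 | no | 0.884 → 0.896 | 5.2 → 5.2% |
| 39 | 1 | no | 0.885 → 0.881 | 5.2 → 4.9% |
| 39 | 2 | no | 0.888 → 0.821 | 5.2 → 5.4% |
| 39 | 2 | yes | 0.791 → 0.785 | 3.1 → 4.5% |

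Mean bias was within ±0.03 in every setting, with or without the weight term. The Monte Carlo error on a 5% rate is √(0.05 × 0.95/4000) = 0.34 points, so no rate shows inflation. In the balanced g=2 settings, the average unadjusted model SE was 0.990 (N=30) and 0.863 (N=39). The ratios to the empirical SE are 0.990/0.920 = 1.08 and 0.863/0.791 = 1.09, so the CI is about 8 to 9% too wide.

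**Step 5: power with the stratum added** (δ 2.5, SD 2.5). Residual SD × √(1−R²), one degree of freedom fewer than the planned model's N−5.

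| N | Planned model | R²=0 | 5% | 10% | 20% |
|---|---|---|---|---|---|
| 30 | 69.9% | 69.8% | 72.0% | 74.3% | 79.1% |
| 39 | 81.6% | 81.5% | 83.4% | 85.4% | 89.1% |

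This formula assumes balanced arms. A separate simulation (5,000 runs per setting) without balancing gives a larger cost at R²=0: 66 → 64% at N=30 and 79 → 78% at N=39. At R²=20% it gives 65 → 73% and 79 → 86%.

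**The case against.** The strongest case against is that this is a covariate preference in an exploratory analysis. Protocol and SAP agree with each other, FMD is outside the key secondary hierarchy, and the planned output is LS means with a 95% CI. Baseline FMD is already in the model, and nothing shows that weight predicts FMD change beyond it. At g=1 the simulated precision gain is nil. Cogstate is analysed in the whole safety population, so fewer terms in 30 to 39 children can be defended. All of this stands, and it sets the severity. It does not supply a reason for the omission, and the documents give none. The exploratory nature of the sub-study is cited only for removing multiple imputation.

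Several stronger readings are tempting but not supported:

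- A reader might infer that weight imbalance biases the treatment estimate. It does not on average. It shifts a single estimate, and only if weight predicts FMD change.
- A reader might infer that the sub-study has no balance on weight. Consent and the baseline scan precede randomisation, so these children are themselves randomised within weight strata. Balance is not guaranteed in a volunteer subset needing both scans, so the 18 to 27% in Step 2 is a worst case.
- A reader might infer that every other ANCOVA adjusts for strata. The multiple-imputation ANCOVA in SAP 2.4.4.1.4 lists no covariates, and SAP Appendix C names only baseline LDL-C for the pattern-mixture analysis, although that sentence omits even treatment group.
- A reader might argue that weight matters because it sets the dose. Phase 2 LDL-C reductions did differ by weight group (Protocol section 4: −40.4% and −49.8% in Cohort 2, −31.9% and −59.8% in Cohort 4), and Appendix E links FMD impairment to LDL-C. But those were treated children. A dose effect exists only on alirocumab and is a treatment-by-weight interaction, which a main effect does not address.

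**Conclusion.** The point holds as a cheap improvement of minor severity. The FMD ANCOVA omits a randomisation stratum that its closest counterpart includes, without explanation. The validity of the planned test is not in question, and the stated power table is unaffected.

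What can be gained is precision and better CI calibration. At an assumed g of 2 points (16% of variance), the standard error at N=30 falls by about 7% (1.02 to 0.95) if weight is unbalanced. If weight is balanced, a test running at about 3% is brought back close to 5%. At 4% of variance or less, there is little or nothing to gain. These sizes rest on assumed weight effects and on a common variance. The model with unequal variances was not simulated.

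**What to change.** Before the first database lock, add the baseline body-weight stratum (<50, ≥50 kg, as recorded in IVRS) as a fixed categorical effect to the FMD ANCOVA in Protocol Appendix E and SAP 2.4.4.4, for both the analysis regardless of adherence and the on-treatment analysis. Report weight stratum by arm in the FMD population. If the sponsor prefers the smaller model, one sentence giving the reason would close the point.

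Prior DFI14223 participation should not enter under a rule that depends on how many such children the sub-study turns out to contain. The simple course is to leave it out and say so. By the Step 5 formula, including it as well would change power by 0.2 points or less.

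The cost is one line of text, no new data and one degree of freedom: about 0 to 2 points of power if weight explains nothing (0.1 by formula, 1 to 2 in simulation). Settling it before lock also avoids choosing a covariate after results are known.
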